**Experimental Design and Methods**

Study population: Total of 18 adults with CF will be recruited from the Colorado CF program at National Jewish Health. Subjects who withdraw early will be replaced until the target n of 18 is achieved.

**Inclusion criteria:**

- 1) Confirmed diagnosis of CF based on the following criteria: Positive sweat chloride ≥60mEq/liter (by pilocarpine iontophoresis) and genotype with two F508del CFTR mutations, and accompanied by one or more clinical features consistent with the CF phenotype
- 2) Male or female subjects ≥ 18 years of age
- 3) FEV1 ≥ 50% predicted (Hankinson)
- 4) Clinically stable without evidence of acute upper or lower respiratory tract infection or current pulmonary exacerbation within the 14 days prior to the screening visit
- 5) Ability to reproducibly perform spirometry (according to ATS criteria)
- 6) Ability to understand and sign a written informed consent or assent and comply with the requirements of the

study

- 7) Willing and able to perform nasal potential difference testing
- 8) No changes in use of nasal medications within 2 weeks of screening visit
- 9) If on Orkambi, has been on stable Orkambi dose for at least 4 weeks at day 1.

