**Exclusion criteria:**

- 1) History of hypersensitivity to sildenafil
- 2) Use of an investigational agent within the 4-week period prior to Visit 1 (Day 0)
- 3) Breastfeeding, pregnant, or verbal expression of unwillingness to practice an acceptable birth control method (abstinence, hormonal or barrier methods, partner sterilization or intrauterine device) during participation in the study
- 4) History of significant hepatic (SGOT or SGPT > 3 times the upper limit of normal at screening, documented biliary cirrhosis, or portal hypertension), cardiovascular (history of aortic stenosis, coronary artery disease, pulmonary hypertension with right ventricular systolic pressure >55 mmHg or life-threatening arrhythmia), neurological (history of stroke), hematologic (history of bleeding diathesis), ophthalmologic (history of retinal impairment or non-arteritic ischemic optic neuritis) or renal impairment (creatinine >1.8 mg/dL.)
- 5) Inability to swallow pills
- 6) Previous lung transplantation
- 7) Use of concomitant nitrates,  $\alpha$ -blocker, or Ca channel blocker
- 8) Use of concomitant medications known to be potent inhibitors of CYP3A4 (e.g. ketoconazole, itraconazole, ritonavir, clarithromycin, erythromycin, rifampin, verapamil)
- 9) Presence of a condition or abnormality that in the opinion of the investigator would compromise the safety of the subject or the quality of the data
- 10) Weight less than 40 kg
- 11) History of sputum or throat swab culture yielding *Burkholderia cepacia* within 2 years of screening
- 12) History of nasal disease or nasal surgery that would, in the opinion of the investigator, impede accurate measurements of NPD
- 13) Use of anticoagulant medication (e.g. heparin, coumadin)
- 14) Resting room air oxygen saturation <93%
- 15) Use of nighttime oxygen
- 15) History of migraine headaches
- 16) Baseline BP of < 90/50 mm Hg

Study Design

This study is a randomized, placebo-controlled, double blind study of sildenafil (Revatio) in clinically stable patients with mild-moderate CF lung disease. The length of participation for each subject will be approximately 6 weeks, and will consist of a screening visit, 4 out-patient visits, and a follow-up phone assessment 2 weeks after subject's study completion.

Randomization

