#### Concomitant medications

All subjects should continue the same medications throughout the study period, as medically feasible, with no introduction of new chronic therapies during or <4 weeks prior to enrollment. If a change in concomitant medications is required, the reason(s) for the change(s) will be recorded on the subject's CRF. Subjects who

require hospitalization for the treatment of a pulmonary exacerbation during the course of the trial will be withdrawn from the study.

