There is no drug interaction between ivacaftor and sildenafil. However, because the lumacaftor portion of Orkambi is a strong inducer of CYP3A, use of Orkambi with sildenafil may decrease sildenafil levels. Based on our previous work, average trough values at steady state for subjects with CF receiving 40 mg of sildenafil t.i.d. were approximately 39 ng/mL. Sildenafil trough levels will be performed at visits 2, 3, and 4 to confirm non-interference of metabolism with co-administration with Orkambi.

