## Statistical analysis

### Sample size

Using PASS 13, data from two consecutive within subject NPD measurements following treatment with placebo in a trial of the Na transport inhibitor QAU145 were used to perform power calculations for this study. Based on a 2.59 mV standard deviation of the change in conductance of the maximal basal PD with placebo, enrollment of 12 (sildenafil) and 6 (placebo) subjects will provide 100% power to detect a 10.4 mV change in maximal basal PD at the 5% significance level. The reported results from the VX-770-101 trial reported at NACFC in 2008 also indicate that this study is well-powered to detect changes in sweat chloride. Based on a standard deviation of 2.6 mEq, enrollment of 12 (sildenafil) and 6 (placebo) subjects will provide 95% power to detect at least a 5 mEq change from placebo at the 5% significance level.

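### Inclusion 9 does not cover a subject who stopped Orkambi shortly before entry; such a subject adds noise, not expected bias, to the 12 vs 6 comparison

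*Combined protocol and SAP*

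**What the plan says.** Inclusion criterion 9: "If on Orkambi, has been on stable Orkambi dose for at least 4 weeks at day 1". The condition at its start limits it to subjects taking the drug at Day 1.

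Other rules that might reach a recent stopper:

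- **Concomitant medications.** The look-back before entry concerns starting drugs only: "with no introduction of new chronic therapies during or <4 weeks prior to enrollment". The continuity clause, "All subjects should continue the same medications throughout the study period, as medically feasible", begins with the study period.
- **Exclusion 2.** It sets a 4-week window, for investigational agents only.
- **Exclusion 9.** It allows exclusion for a condition or abnormality that "in the opinion of the investigator would compromise the safety of the subject or the quality of the data". This is a judgment, not a rule on modulators.
- **Inclusion 8.** For nasal drugs the wording is broader: "No changes in use of nasal medications within 2 weeks of screening visit". That covers starts, stops and dose changes.

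All subjects must carry two F508del mutations. Outcome measurements and Procedures warns that "use of Orkambi with sildenafil may decrease sildenafil levels", because lumacaftor induces CYP3A. The primary endpoint is the within-subject change in maximum basal PD, and sweat chloride is secondary. No stratification by Orkambi use, or adjustment for it, is stated.

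**The concern.** By asking for four stable weeks, the plan implies that a recent change in Orkambi could disturb what the trial measures. The same reasoning applies to stopping, but the rule omits it. Screening may fall as late as Day 0, so a subject could stop a few days earlier, satisfy every mandatory criterion, and have the baseline NPD, sweat test, lung clearance index and spirometry while any modulator effect is wearing off. The Day 29 values would then be taken without it.

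Two things are at stake. First, one drifting subject carries weight in a comparison of 12 with 6. Second, fading CYP3A induction could change sildenafil levels during treatment. That happens only in subjects who receive sildenafil, so the placebo arm does not balance it. An analysis by current Orkambi use would not identify the subject, who would be coded as a non-user.

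**Working it through.** **Inputs from Sample size.** Sweat chloride: SD 2.6 mEq, effect 5 mEq against placebo, 12 and 6 subjects, 5% level. The plan states that "enrollment of 12 (sildenafil) and 6 (placebo) subjects will provide 95% power to detect at least a 5 mEq change from placebo". Maximal basal PD: SD 2.59 mV, effect 10.4 mV, stated power 100%.

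**Assumptions.** One recent stopper among the 18, with a drift s of 5, 10 or 15 mEq from baseline to Day 29 in the unfavourable direction. The documents give neither figure. The test is a two-sided pooled t test. The plan does not state sidedness, but this choice reproduces its power.

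**Step 1: the plan's own figures.** SE = 2.6 × √(1/12 + 1/6) = 2.6 × 0.5 = 1.30. Noncentrality = 5/1.30 = 3.85 on 16 df, which gives 95.0% power. For maximal basal PD the same method gives 100.0%. Both match.

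**Step 2: expected bias.** A stopper on sildenafil moves the sildenafil-minus-placebo difference by s/12. A stopper on placebo moves it by s/6 the other way. Allocation is 2:1 and independent of stopping, so the expected shift is (2/3)(s/12) − (1/3)(s/6) = s/18 − s/18 = 0.

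**Step 3: added variance.** The variance of that shift is (2/3)(s/12)² + (1/3)(s/6)² = s²/216 + s²/108 = s²/72. So SE = √(1.69 + s²/72), which is 1.43, 1.75 and 2.19 for s = 5, 10 and 15.

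**Step 4: sweat chloride power and type I error, by simulation.**

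| Drift (mEq) | Power, stopper on sildenafil | Power, stopper on placebo | Power, averaged 2:1 | Type I error, on sildenafil | Type I error, on placebo | Type I error, averaged |
|---|---|---|---|---|---|---|
| 5 | 87% | 98% | 91% | 4% | 6.7% | 4.9% |
| 10 | 63% | 98% | 75% | 2.3% | 8.5% | 4.3% |
| 15 | 27% | 98% | 50% | 1.0% | 8.1% | 3.3% |

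The averages are (2 × sildenafil + placebo)/3. For 10 mEq, (2 × 63 + 98)/3 = 74.7%.

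**Step 5: primary endpoint.** With one stopper drifting 5, 10 or 15 mV, power for 10.4 mV stays at about 99.9% or more.

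**Step 6: chance imbalance with two stoppers.** The probability that both fall in the same arm is (66 + 15)/153 = 53%.

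The effect of fading CYP3A induction is not quantified, because the documents give no figure for it.

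**The case against.** A reader might infer that loss of the modulator effect is counted as a treatment effect. The documents do not support that for the comparison between arms. The trial is randomized, double blind and placebo-controlled, and stopping before randomization is independent of arm. The raised false-positive rate of about 7% to 8.5% appears only if the stopper lands on placebo, a one-in-three event. In the other two thirds the rate falls below 5%. A before-and-after reading within one arm would lack this protection. The crossover analysis named in Data Analysis does not fit the parallel arms described, but that is a separate problem.

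Other points on this side also stand:

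- Drift size, speed of fading and frequency of stopping are all undocumented. A drift of 15 mEq is three times the target effect.
- The primary endpoint is practically unaffected.
- Subjects screened at Day −14 who had stopped before screening would be about two weeks off drug at baseline.
- An investigator could use exclusion 9. Trough levels at visits 2 to 4 give some view of exposure.
- The plan allows rank-based tests if data are non-normal. In the worst case above (15 mEq, stopper on sildenafil), a rank-sum test keeps about 75% power, against 27% for the t test.

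These points limit the consequence. They do not close the gap: the safeguards are discretionary or come after the data are collected, and the rule costs little to complete.

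**Conclusion.** The gap in inclusion 9 is real: a subject who stopped Orkambi shortly before Day 1 is eligible under every mandatory criterion. The consequence is loss of precision and possible chance imbalance. Expected bias is zero, and type I error averaged over allocation does not exceed 5%.

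The practical loss is in sweat chloride, a secondary endpoint: 4, 20 or 45 points of power for one stopper under the three assumed drifts. These figures depend on at least one such subject being enrolled and on drifts that the documents do not supply. With no recent stopper there is no loss. A shift in sildenafil exposure, confined to the active arm, is a further possibility that follows from the plan's own statement about lumacaftor. This is a cheap improvement to one criterion, not a threat to the primary analysis.

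**What to change.** Reword inclusion 9 to: *Has not started, stopped or changed the dose of Orkambi within 4 weeks before Day 1.* This keeps the plan's own window and brings the criterion into line with inclusion 8, which already covers any change.

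Do not extend the Concomitant medications section to discontinuation of all chronic therapies. That would delay subjects who stopped unrelated drugs, in an 18-subject trial recruiting from one program, and this point gives no reason for it.

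The cost is one sentence. A subject who recently stopped Orkambi enters up to 4 weeks later. Sample size and stated power do not change.

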**Exclusion criteria:**

- 1) History of hypersensitivity to sildenafil
- 2) Use of an investigational agent within the 4-week period prior to Visit 1 (Day 0)
- 3) Breastfeeding, pregnant, or verbal expression of unwillingness to practice an acceptable birth control method (abstinence, hormonal or barrier methods, partner sterilization or intrauterine device) during participation in the study
- 4) History of significant hepatic (SGOT or SGPT > 3 times the upper limit of normal at screening, documented biliary cirrhosis, or portal hypertension), cardiovascular (history of aortic stenosis, coronary artery disease, pulmonary hypertension with right ventricular systolic pressure >55 mmHg or life-threatening arrhythmia), neurological (history of stroke), hematologic (history of bleeding diathesis), ophthalmologic (history of retinal impairment or non-arteritic ischemic optic neuritis) or renal impairment (creatinine >1.8 mg/dL.)
- 5) Inability to swallow pills
- 6) Previous lung transplantation
- 7) Use of concomitant nitrates,  $\alpha$ -blocker, or Ca channel blocker
- 8) Use of concomitant medications known to be potent inhibitors of CYP3A4 (e.g. ketoconazole, itraconazole, ritonavir, clarithromycin, erythromycin, rifampin, verapamil)
- 9) Presence of a condition or abnormality that in the opinion of the investigator would compromise the safety of the subject or the quality of the data
- 10) Weight less than 40 kg
- 11) History of sputum or throat swab culture yielding *Burkholderia cepacia* within 2 years of screening
- 12) History of nasal disease or nasal surgery that would, in the opinion of the investigator, impede accurate measurements of NPD
- 13) Use of anticoagulant medication (e.g. heparin, coumadin)
- 14) Resting room air oxygen saturation <93%
- 15) Use of nighttime oxygen
- 15) History of migraine headaches
- 16) Baseline BP of < 90/50 mm Hg

Study Design

This study is a randomized, placebo-controlled, double blind study of sildenafil (Revatio) in clinically stable patients with mild-moderate CF lung disease. The length of participation for each subject will be approximately 6 weeks, and will consist of a screening visit, 4 out-patient visits, and a follow-up phone assessment 2 weeks after subject's study completion.

Randomization

Subjects will be randomized in a 2:1 fashion to sildenafil or placebo. The randomization protocol will be created by [name] (Professor and Head, Division of Biostatistics and Bioinformatics, National Jewish Health). The protocol will be provided directly to the study pharmacist, who will communicate randomization to the coordinator at the research site.

Dosing

During the course of the study, patients will receive 4 weeks of therapy: 28 days of placebo orally t.i.d. or 28 days of days of sildenafil orally t.i.d. Dosing of sildenafil will be escalated weekly (20 mg orally t.i.d for the first week, 40 mg orally t.i.d. for the second through fourth weeks.) Patients receiving placebo will have sham dose escalation to maintain blinding. Patients not tolerating dose escalation will be discontinued from the study.

Screening visit (visit 1; Day -14-0):

Prior to conducting any study-related activities, written informed consent/assent will be obtained, signed and dated by the subject and/or parent/guardian.

A medical history including diagnosis of CF, current medications and other relevant past medical history will be obtained, and a complete physical exam will be performed by the principal investigator including nasal exam rating (NER), height, weight, temperature, blood pressure, respirations and baseline pulse oximetry will be recorded. Any abnormal findings will be documented. Clinical laboratory tests will be performed including CBC with differential, chemistry profile, INR (total of 10cc of blood), and a urine pregnancy test (for females of child-bearing potential). A baseline EKG will be obtained. Subjects will undergo spirometry according to ATS criteria.

Initiation visit period 1 (visit 2; Day 1): Subjects meeting entry criteria will be evaluated in the outpatient research unit. CFR-Q will be administered. A limited physical exam will be performed to include vital signs and NER. A urine pregnancy test will be done for females of child-bearing potential. eNO and spirometry will be performed. Spontaneously expectorated sputum will be collected. Safety labs and a sildenafil trough level will be drawn. Each subject will undergo pilocarpine iontophoresis with sweat collection, nasal potential difference testing, and lung clearance index testing. Patient will then receive study medication (placebo or sildenafil.) Subsequent to medication dosing, vital signs will be assessed at 1 hour and 2 hours post-dose. A drop in systolic blood pressure of  $\geq 20$ mmHg will be considered intolerance, and the subject will be discontinued from the study.

Subjects tolerating the medication will be discharged with a 7-day supply of placebo or sildenafil 20 mg p.o. t.i.d. Subjects will be instructed to call the study staff (during business hours) or the pulmonary attending on call (after business hours) for any significant adverse events that occur (e.g. severe headache, dizziness, or persistent visual changes.)

Study visit (visit 3; Day 8 $\pm$ 3): After 7 days of therapy, the subject will return to the study site. Vitals signs and adverse events will be assessed. Safety labs and a sildenafil trough level will be drawn. Each subject will undergo pilocarpine iontophoresis with sweat collection, nasal potential difference testing, and lung clearance index testing. Medication bottles will be collected. Subject will then receive study medication (placebo or sildenafil 40 mg). Subsequent to medication dosing, vital signs will be assessed 1 hour and 2 hours post-dose. A drop in systolic blood pressure of  $\geq 20$ mmHg will be considered intolerance. Subjects with intolerance of dose escalation will be discontinued from the study. Subjects tolerating medication will be given 21 days of placebo or sildenafil 40 mg p.o. t.i.d.

Study visit (visit 4; Day 29 $\pm$ 3): Subjects will return to the study site for visit 4. CFR-Q will be administered. A complete physical exam will be performed to include vital signs and NER, and adverse events will be assessed. eNO and spirometry will be performed. Spontaneously expectorated sputum will be collected. Safety labs and a sildenafil trough level will be drawn. Each subject will undergo pilocarpine iontophoresis with sweat collection, nasal potential difference testing, and lung clearance index testing. Clinical laboratory tests will be performed including CBC with differential, chemistry profile, INR (total of 10cc of blood), and a urine pregnancy test (for females of child-bearing potential). Medication bottles will be collected.

Study visit (visit 5; Day 43 $\pm$ 3): Two weeks following study completion, the research coordinator will call subjects to determine if any adverse events have occurred or if there have been any changes in concomitant medications.

#### Early Withdrawal

In case of early withdrawal, an Early Withdrawal Visit will be scheduled within 7 days following the last dose of study medication. Physical exam will be performed by the primary investigator including weight, temperature, blood pressure, respirations and pulse oximetry. Spirometry will be performed. Subject will undergo pilocarpine iontophoresis with sweat collection, nasal potential difference testing, and lung clearance index testing. Any abnormal findings will be documented. Clinical laboratory tests will be performed including CBC with differential, chemistry profile, and urine pregnancy test (for females of child-bearing potential.) Medication bottles will be collected.

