### Pharmacokinetics of sildenafil

Sildenafil is rapidly absorbed following oral administration in the fasting state with peak plasma concentrations occurring within 30-120 minutes (median 60 minutes) of administration. It is metabolized by the hepatic microsomal isoenzymes, CYP3A4 and cytochrome p450 2C9 (CYP2C9) to its major metabolite N-desmethyl sildenafil. The metabolite accounts for approximately 20% of the pharmacologic effects of sildenafil. Both sildenafil and N-desmethyl sildenafil have a half-life of approximately 4 hours.

Sildenafil (Revatio®) is FDA-approved for treatment of pulmonary hypertension at an oral dose of 20 mg three times per day. In a large trial (n=278) of use of sildenafil for pulmonary hypertension published in the *New England Journal of Medicine*, escalating doses of sildenafil were used for 12 weeks (20 mg three times a day, 40 mg three times a day, and 80 mg three times per day.) There was no dose-related effect on the primary outcome. Although the initial group of subjects was treated for 12 weeks, improvements in the primary outcome were seen at 4 weeks.

In summary, laboratory evidence that sildenafil can correct the pH and sodium abnormality in CF cells, improve F508del CFTR trafficking and potentiate CFTR dependent Cl transport, and may also exhibit anti inflammatory properties, combined with the well-established safety profile of sildenafil in severe lung disease make it an attractive agent to study in patients with CF. To date, studies have examined the *in vitro* ability of sildenafil to improve ion transport in the setting of abnormal CFTR; we propose to evaluate effects in human CF subjects.

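### Visits 3 and 4 set no dose-to-test interval and their windows can outrun the dispensed supply, so a scheduled NPD can fall about 3 days or more after the last dose; Early Withdrawal values have no analysis rule

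*Combined protocol and SAP*

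**What the plan says.** **Drug kinetics.** The section on pharmacokinetics states: "Both sildenafil and N-desmethyl sildenafil have a half-life of approximately 4 hours".

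**Supply.** At Visit 2, "Subjects tolerating the medication will be discharged with a 7-day supply of placebo or sildenafil 20 mg p.o. t.i.d". At Visit 3 the bottles are collected and 21 days of 40 mg or placebo are handed out. The total of 28 days matches the Dosing section.

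**Scheduled tests.** Visit 3 lists a trough draw, then sweat, NPD and lung clearance index (LCI), and only afterwards "Subject will then receive study medication (placebo or sildenafil 40 mg"). Visit 4 says "Safety labs and a sildenafil trough level will be drawn" and lists the same three tests, with no clinic dose and nothing about that day's home dose. The section on outcome measurements adds: "Sildenafil trough levels will be performed at visits 2, 3, and 4". No section gives hours since the last dose. The visit text allows Visit 3 on Day 8 ± 3 and Visit 4 on Day 29 ± 3. The flowchart prints Visit 4 as 29+3.

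**Early Withdrawal.** Here "an Early Withdrawal Visit will be scheduled within 7 days following the last dose of study medication", and "Subject will undergo pilocarpine iontophoresis with sweat collection, nasal potential difference testing, and lung clearance index testing". The Study population paragraph replaces subjects who withdraw until 18 is reached. The Data Analysis section names no visit for the primary outcome and no analysis set, and it has no rule for Early Withdrawal values. The flowchart has no column for that visit.

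**The concern.** The primary endpoint, change in maximal basal PD, is meant to show what systemic sildenafil does to ion transport. That requires the post-baseline NPD to be taken at a known and similar exposure in the 12 treated subjects. The plan orders a trough but does not turn it into an interval, and its own windows let the tablets run out before the test. A subject can follow the protocol exactly, be tested after days without drug, and be counted as on treatment.

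If the effect fades with the drug, such values dilute the difference and add spread in a small arm. The trough levels suffer too. They are meant to show whether Orkambi lowers sildenafil, and a low level cannot be interpreted without the time of the last dose.

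The Early Withdrawal tests raise a smaller question: they are collected, possibly well after drug has cleared, and nothing says what they are for.

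**Working it through.** **1. Supply against visit windows.** Inputs: Day 1 start, 7 and 21 days dispensed, windows as in the visit text. Assumptions: every dose taken, no spare tablets, Visit 2 bottles returned at Visit 3. A clinic dose on top of the dispensed bottle adds only one dose.

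Full days without supply before Visit 3 = Visit 3 day − (1 + 7).
Full days without supply before Visit 4 = Visit 4 day − (Visit 3 day + 21).
Negative results count as 0.

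| Visit 3 | Visit 4 | Gap before Visit 3 | Gap before Visit 4 |
|---|---|---|---|
| Day 8 | Day 29 | 0 | 0 |
| Day 11 | Day 32 | 11 − 8 = 3 | 32 − 32 = 0 |
| Day 8 | Day 32 | 0 | 32 − 29 = 3 |
| Day 5 | Day 29 | 0 | 29 − 26 = 3 |
| Day 5 | Day 32 | 0 | 32 − 26 = 6 |

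There is no gap on the nominal days. A Visit 3 on Day 9, 10 or 11 leaves 1, 2 or 3 days. Any spacing of more than 21 days between Visits 3 and 4 leaves a gap before Visit 4. Reading the flowchart's 29+3 as Day 29 to Day 32 removes the early dates and keeps the gaps.

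**2. Drug remaining.** Fraction = 0.5^(hours/4), assuming simple exponential decline at the stated half-life.

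| Hours since last dose | Half-lives | Remaining |
|---|---|---|
| 8 | 2 | 25% |
| 12 | 3 | 12.5% |
| 24 | 6 | 1.6% |
| 72 | 18 | 0.0004% |
| 168 | 42 | about 2 × 10⁻¹³ (as a fraction) |

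Two protocol-compliant tests, one at 8 hours and one at 72 hours, differ in expected level by 2^((72 − 8)/4) = 2^16 = 65,536-fold.

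**3. The plan's power figures.** A two-sided two-sample t-test at 5% with 12 and 6 subjects (noncentral t, 16 degrees of freedom) gives over 99.99% for 10.4 mV with SD 2.59, and 95.02% for 5 mEq with SD 2.6. The stated 100% and 95% are reproduced.

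**4. Dilution, as illustration.** Suppose k of the 12 sildenafil subjects are tested with no remaining effect and analysed as treated. The mean difference becomes d × (12 − k)/12; at k = 2 that is 10.4 × 10/12 = 8.67 mV and 5 × 10/12 = 4.17 mEq. Power from 40,000 simulated t-tests per case:

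| k | Maximal basal PD | Sweat chloride |
|---|---|---|
| 0 | about 100% | 95% |
| 1 | about 100% | 87% |
| 2 | 99.8% | 75% |
| 3 | 97.8% | 61% |
| 4 | 88% | 47% |

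The documents give neither the number of late visits nor a withdrawal rate, so k is unknown. Zero remaining effect is the worst case.

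**The case against.** - **A trough is a pre-dose sample.** The Visit 3 order supports this, and Visit 4 lists the draw and tests in the same sequence. Testing near peak would therefore be a deviation from the plan. This stands, and it limits the point at the short end. It does not limit the long end: a pre-dose sample can be taken 8 hours or 3 days after the last dose. The Visit 2 trough, drawn before any study drug, shows that the word carries no interval.
- **Exposure is measured at each NPD visit.** True and useful. But a low level does not show whether the cause is Orkambi, missed doses or an empty bottle. The time of the last dose would.
- **Plasma half-life is not duration of effect.** This stands. The proposed mechanisms include ENaC processing and CFTR trafficking, and the documents give no offset time for either. For the same reason, a reader who infers a 24-hour limit for a valid test finds no basis for it in the documents.
- **NPD conduct follows SOP 528.01**, which is not in the documents and may set timing. That remains open.
- **Early Withdrawal.** A reader might infer that the trial records off-drug Early Withdrawal values as treatment outcomes. The documents do not say so: the values are collected, withdrawn subjects are replaced, and the analysis is silent. What is missing is a rule. Excluding late values also sets aside data from subjects who stopped treatment, which is a reason to state the rule openly.
- **Dose comparison.** A reader might also infer that mixed timing spoils a comparison of 20 mg at Visit 3 with 40 mg at Visit 4. No such comparison is planned.

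**Conclusion.** The point holds for the scheduled visits as more than missing detail. The stated windows and supplies, followed exactly, allow NPD, sweat and LCI anywhere from hours to about 3 days after the last dose, and 6 days in the extreme, with all of these values treated alike as on treatment. This rests on full adherence and no spare tablets. Missed doses would leave tablets over and shorten the gap.

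The consequence is possible dilution and extra variability, of unknown size because the offset of the effect is not given. On the plan's own figures the primary comparison has ample margin; the secondary sweat chloride comparison has little. The change is worth making, but the trial does not stand or fall on it.

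For Early Withdrawal the finding is only that the use of the values is unstated.

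**What to change.** 1. **Dose-to-test interval.** At Visits 3 and 4, require the trough draw and the start of NPD and sweat collection to fall within one interval after the last dose, the same at both visits and chosen by the sponsor. Record the clock time of the last dose. Rebook within the visit window if the interval is missed. Describe the result as the effect at that time, or at trough if testing stays pre-dose.
2. **Windows and supply.** Reconcile the Visit 3 and Visit 4 windows with the 7-day and 21-day supplies, and the flowchart's 29+3 with the ± 3 in the visit text.
3. **Early Withdrawal.** Record the time since the last dose and flag values as off-treatment where that applies. State before database lock that they are not used as the on-treatment post-baseline value in the primary comparison.

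The cost is a few sentences of protocol text, one CRF field and some rebooked visits.
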